Dose Modifications – Phase 1 dose escalation (ALRN-6924 administered as single agent therapy)

In the event a Grade 4 AE considered related to ALRN-6924 is observed, the patient must be discontinued from the study. Exceptions include Grade 4 neutropenia lasting <3 days, and emesis, diarrhea or electrolyte abnormalities that resolve within 2 days on optimum treatment. For these exceptions, treatment may be delayed for up to 2 weeks to allow resolution of the toxicity (i.e., return to Grade ≤ 1 or baseline), followed by re-treatment at a reduced dose. Two dose reductions are permitted, a third dose reduction will require evidence of clinical benefit and approval by the Medical Monitor. Relevant labs should be repeated as medically indicated.

In the event a Grade 3 AE considered related to ALRN-6924 is observed (exceptions are Grade 3 fatigue, nausea, emesis, diarrhea or clinically insignificant electrolyte abnormalities that resolve within 2 days on optimum treatment), treatment may be delayed for up to 2 weeks to allow resolution of the toxicity, followed by re-treatment at a reduced dose. Two dose reductions are permitted, a third dose reduction will require evidence of clinical benefit and approval by the Medical Monitor. Relevant labs should be repeated as medically indicated.

Following related Grade 3 and Grade 4 AEs (as permitted), the dose for re-treatment will be reduced by 25% intervals (e.g., if the dose is 3.1 mg/kg, the dose will be reduced sequentially to 2.3 mg/kg and 1.7 mg/kg).

For other clinically significant AEs, treatment may be delayed by up to 2 weeks to allow for the resolution of AEs to an acceptable level, and a dose reduction may be made as described above at the discretion of the Investigator in consultation with Sponsor's Medical Monitor. If a patient experiences multiple AEs, decisions on dosing delay or dose reduction will be based on the most severe AE. Any patient who experiences recurrent, clinically significant AEs after one dose reduction may undergo one additional dose reduction. Patients who continue to experience clinically significant AEs after a 2-week delay or the maximum allowed number of dose reductions will be discontinued from study treatment.

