- Hemoglobin $< 8 \text{ g/dL}$ and $> 6 \text{ g/dL}$

After resolution of hematologic toxicity (i.e., return to Grade ≤ 1 or baseline), patients may continue at a reduced dose. Relevant labs should be repeated as medically indicated.

Following related Grade 3 and Grade 4 AEs (as permitted), the dose for re-treatment will be reduced by 25% intervals (e.g., if the dose is 3.1 mg/kg, the dose will be reduced sequentially to 2.3 mg/kg and 1.7 mg/kg). Two dose reductions are permitted, a third dose reduction will require evidence of clinical benefit and approval by the Medical Monitor.

Dose Modifications – Phase 2a dose expansion in MDM2 amplified or MDM2/CDK4 co-amplified solid tumors (ALRN-6924 plus palbociclib)

Dose modifications of ALRN-6924 will be as described above for the Phase 1 dose escalation. Dose modifications of palbociclib are to be made in accordance with the current approved US prescribing information. In the event that palbociclib administration must be discontinued, the patient may continue to receive ALRN-6924 as a study participant until a criterion for treatment discontinuation has been met. However, if discontinuation of ALRN-6924 is required, patients will be considered to have discontinued study treatment. These patients may continue to receive palbociclib treatment at the investigator's discretion.

Dose Limiting Toxicity Definition during Phase 1 Dose Escalation

A DLT will be defined as any Grade ≥ 3 AE that is considered possibly, probably, or definitely related to the study drug, with the following exceptions: (1) for fatigue, nausea, emesis, diarrhea or mucositis, only Grade ≥ 3 AE that do not respond within 48 hours to standard supportive/pharmacological treatment will be considered DLT; (2) for electrolyte imbalances, only Grade ≥ 3 AE that do not respond to correction within 24 hours will be considered DLT; (3) for infusion reactions, only a Grade 3 reaction which caused hospitalization or Grade 4 will be considered DLT. In addition, specific hematologic DLTs are defined as:

- Thrombocytopenia – Grade 4 of any duration, Grade 3 for ≥ 7 days, or Grade 3 associated with clinically significant bleeding
- Neutropenia – Grade 4 for ≥ 3 days, or any Grade ≥ 3 febrile neutropenia

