Phase 2a – Dose Expansion in MDM2 Amplified or MDM2/CDK4 Co-amplified Solid Tumors (ALRN-6924 plus palbociclib)

Patients enrolled in this cohort must have MDM2 amplified or MDM2/CDK4 co-amplified solid tumors, as determined by local, commercial or central assays such as NGS, fluorescent in situ hybridization (FISH) or comparative genomic hybridization (CGH). However, all patients must have fresh or archival tissue submitted to the central laboratory for NGS testing. The central laboratory's results will determine the patient's official classification as MDM2 amplified, MDM2/CDK4 co-amplified, or neither MDM2 amplified nor MDM2/CDK4 co-amplified.

Mutational analysis of TP53 is not required for this cohort, as TP53 mutations are extremely rare among patients with MDM2 amplifications. However, patients with known mutations or deletions of TP53 will be excluded from study participation. Likewise, patients with known Rb mutations will be excluded, as the cell cycle arrest and senescence response by palbociclib's CDK4/6 inhibition is mediated by Rb, and loss or functional mutation of Rb is specifically associated with resistance to palbociclib.³⁰

Enrollment of the first 3 patients in this cohort will be separated in time by at least one week each, to assess for unexpected acute toxicities related to administration of the treatment regimen. ALRN-6924 will be administered by IV infusion over 1 hour (\pm 15 min) on Days 1, 8, and 15 of a 28-day cycle. Palbociclib

will be administered at an oral dose of 100 mg daily for 21 days (one dose level below the approved oral dose of 125 mg) in the same 28-day cycle. A safety run-in group of 6-8 patients will first be enrolled and evaluated before further patients are permitted to enroll. In the event that this regimen is not determined to be safe or tolerable at these dose levels, the dose of ALRN-6924 will be decreased by 25% and/or the dose of palbociclib will be decreased by one dose level (to 75 mg/day), as needed based on the pattern of toxicities encountered. An additional 6-8 patients will be assessed in a safety run-in using the reduced dose level before further enrollment is permitted. One subsequent reduction of the ALRN-6924 dose by 25% may be implemented, if safety and tolerability are still not acceptable. Once the safety run-in is complete, all subsequent patients will be enrolled at the recommended dose level.

Phase 1 and Phase 2a

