ALRN-6924 and palbociclib have not previously been co-administered in humans. Therefore, for the Phase 2a cohort of patients with MDM2 amplified or MDM2/CDK4 co-amplified solid tumors, a safety run-in group of 6-8 patients will first be enrolled and evaluated by the sponsor and the primary investigators before further patients are permitted to enroll. The SRC will use the DLTs defined in Phase 1 and the toxicity profile of palbociclib (in accordance with the package insert) as a guide for assessing safety.

Enrollment of the first 3 patients in this cohort will be separated in time by at least one week each, to assess for unexpected acute toxicities related to administration of the treatment regimen. Patients will receive ALRN-6924 at the previously determined recommended Phase 2 dose for the once-weekly administration schedule (3.1 mg/kg on Days 1, 8, and 15) and palbociclib at an oral dose of 100 mg daily for 21 days (one dose level below the approved oral dose of 125 mg) in a 28-day cycle. In the event that this regimen is not determined to be safe or tolerable at these dose levels, the dose of ALRN-6924 will be decreased by 25% and/or the dose of palbociclib will be decreased by one dose level (to 75 mg/day), as needed based on the pattern of toxicities encountered, and an additional 6-8 patients will be assessed in a safety run-in using the reduced dose level, before further enrollment is permitted. Subsequent reductions of the ALRN-6924 dose by 25% may be implemented if safety and tolerability are still not acceptable. The decision to begin palbociclib below the approved dose level is based on the frequency of required dose reductions, often due to neutropenia. The SRC may consider adjusting to the approved palbociclib dose, if palbociclib-related toxicities are not prohibitive and patient benefit is expected to outweigh risk. Once the safety run-in is complete, all subsequent patients will be enrolled at the recommended dose level.

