5.8 Dose and Schedule Adjustments for Toxicity

5.8.1 Dose Modifications – Phase 1 dose escalation (ALRN-6924 administered as single agent therapy)

In the event a Grade 4 AE considered related to ALRN-6924 is observed, the patient must be discontinued from study treatment. Exceptions include Grade 4 neutropenia lasting <3 days, and emesis, diarrhea or electrolyte abnormalities that resolve within 2 days on optimum treatment. For these exceptions, treatment may be delayed for up to 2 weeks to allow resolution of the toxicity (i.e., return to Grade ≤ 1 or baseline), followed by re-treatment at a reduced dose. Two dose reductions are permitted; a third dose reduction will require evidence of clinical benefit and approval by the Medical Monitor. Relevant labs should be repeated as medically indicated.

In the event a Grade 3 AE considered related to ALRN-6924 is observed (exceptions are Grade 3 fatigue, nausea, emesis, diarrhea or clinically insignificant electrolyte abnormalities that resolve within 2 days on optimum treatment), treatment may be delayed for up to 2 weeks to allow resolution of the toxicity, followed by re-treatment at a reduced dose. Two dose reductions are permitted, a third dose reduction will require evidence of clinical benefit and approval by the Medical Monitor. Relevant labs should be repeated as medically indicated.

Dose modifications for re-treatment following related Grade 3 and Grade 4 AEs (as permitted): patients will be re-treated at the preceding dose level (per Figure 9).

For other clinically significant AEs, treatment may be delayed by up to 2 weeks to allow for the resolution of AEs to an acceptable level, and may continue treatment at a reduced dose level as described above at the discretion of the Investigator in consultation with Sponsor's Medical Monitor. If a patient experiences multiple AEs, decisions on dosing delay or dose reduction will be based on the most severe AE. Any patient who experiences recurrent, clinically significant AE after one dose reduction may undergo one additional dose reduction. Patients who continue to experience clinically significant AEs after a 2-week delay or the maximum allowed number of dose reductions will be discontinued from the study.

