- Platelet counts $< 25 \times 10^9/L$ and $> 10 \times 10^9/L$, or
- Hemoglobin $< 8\text{ g/dL}$ and $> 6\text{ g/dL}$

After resolution of hematologic toxicity (i.e., return to Grade ≤ 1 or baseline), patients may continue at a reduced dose. Relevant labs should be repeated as medically indicated.

Following related Grade 3 and Grade 4 AEs (as permitted), the dose for re-treatment will be reduced by 25% intervals (e.g., if the dose is 3.1 mg/kg, the dose will be reduced sequentially to 2.3 mg/kg and 1.7 mg/kg). Two dose reductions are permitted, a third dose reduction will require evidence of clinical benefit and approval by the Medical Monitor.

5.8.3 Dose Modifications – Phase 2a Dose Expansion in MDM2 Amplified or MDM2/CDK4 Co-amplified Solid Tumors (ALRN-6924 plus palbociclib)

Dose modifications of ALRN-6924 will be as described in Section 5.8.1. Dose modifications of palbociclib should be made in accordance with the current approved US prescribing information.

In the event that palbociclib administration must be discontinued, the patient may continue to receive ALRN-6924 as a study participant until one of the criteria for treatment discontinuation has been met. However, if discontinuation of ALRN-6924 is required, patients will be considered to have discontinued study treatment. Those patients may continue to receive palbociclib treatment at the Investigator's discretion.

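### The synopsis and Section 5.8.1 give different ALRN-6924 re-treatment doses after the same toxicity (2.3 against 2.1 mg/kg from 3.1 mg/kg), and the palbociclib combination cohort is referred to both

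*Protocol*

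**What the plan says.** Two parts of the current protocol deal with re-treatment of Phase 1 patients after a related Grade 3 event or one of the excepted Grade 4 events.

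- **Synopsis, Dose Modifications, Phase 1:** "the dose for re-treatment will be reduced by 25% intervals". Its worked example starts at 3.1 mg/kg and steps to 2.3 and then 1.7 mg/kg.
- **Section 5.8.1:** "patients will be re-treated at the preceding dose level (per Figure 9"). No percentage and no dose is given.

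The combination cohort has no rule of its own and is referred elsewhere, to a different place in each part of the document.

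- **Synopsis, combination cohort:** "Dose modifications of ALRN-6924 will be as described above for the Phase 1 dose escalation". This leads to the 25% rule.
- **Section 5.8.3:** "Dose modifications of ALRN-6924 will be as described in Section 5.8.1". This leads to the preceding-level rule.

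The PTCL expansion has no such conflict. The synopsis and Section 5.8.2 both use 25% steps with the same example: "if the dose is 3.1 mg/kg, the dose will be reduced sequentially to 2.3 mg/kg and 1.7 mg/kg".

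Section 5.7.2 starts the combination at 3.1 mg/kg of ALRN-6924 on Days 1, 8 and 15. If the run-in shows that the regimen is not tolerable, "the dose of ALRN-6924 will be decreased by 25" percent and/or palbociclib is lowered. Section 3.2 adds: "One subsequent reduction of the ALRN-6924 dose by 25% may be implemented".

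**The concern.** The trigger and the patients are the same, but the instructions differ, and no statement gives one text precedence. The dose a patient gets after a given toxicity can therefore depend on which section the site consults. Both texts bar re-escalation once a dose has been cut, so the choice persists for that patient. Both also refer back to the same reduction rule for other clinically significant events and for patients who have had a DLT, so the conflict extends beyond one sentence.

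The combination cohort is an important place for this to arise. The two drugs had not been given together in humans before, a run-in of 6 to 8 patients decides whether enrolment continues, and Section 5.7.2 itself expects frequent palbociclib reductions for neutropenia. Mixed re-treatment doses in so small a group would blur the tolerability record after the first reduction.

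The stakes have limits. Whether a Cycle 1 event counts as a DLT does not depend on the later re-treatment dose, and summaries of dose actually received stay valid.

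**Working it through.** **Inputs, all printed in the protocol**

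- Synopsis example: 3.1, then 2.3, then 1.7 mg/kg.
- Section 5.7.2: DL-6A = 3.1 mg/kg; DL-5A = 2.1 mg/kg.
- Section 5.7.1: DL-1 = 0.16 mg/kg; 100% steps through DL-4A, then 67%, 50%, 40%, 33% from DL-5A; level 7A-2 = 4.4 mg/kg.
- Combination starting dose: 3.1 mg/kg.

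**Reproducing the synopsis example**

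- 3.1 × 0.75 = 2.325, printed as 2.3.
- 2.325 × 0.75 = 1.744, printed as 1.7.

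Taking 25% of the starting dose each time would give 3.1 × 0.50 = 1.55 at the second step. The printed example is therefore multiplicative.

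**First reduction from 3.1 mg/kg (needs no figure)**

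| Text | Re-treatment dose | Change from 3.1 |
|---|---|---|
| Synopsis, 25% rule | 2.3 mg/kg | −25% nominal; 2.3/3.1 − 1 = −25.8% as printed |
| Section 5.8.1, preceding level (DL-5A) | 2.1 mg/kg | 2.1/3.1 − 1 = −32.3% |

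Gap: 2.3 − 2.1 = 0.2 mg/kg; 0.2/3.1 = 6.5% of the starting dose.

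**Plausibility of the ladder**

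- DL-4A: 0.16 × 2 × 2 × 2 = 1.28.
- DL-5A: 1.28 × 1.67 = 2.14 (printed 2.1).
- DL-6A: 2.1 × 1.5 = 3.15 (printed 3.1).
- DL-7A-2: 3.1 × 1.4 = 4.34 (printed 4.4).

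The printed levels follow the stated increments closely but not exactly.

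**Conditional figures**

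Figure 9 was not reproduced in the text I worked from, so each of these rests on the assumption given.

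1. *Second reduction from 3.1 mg/kg.* The synopsis gives 1.7. Under Section 5.8.1 it would be DL-4A, which the text does not print. Working forward gives 1.28. Working back gives 2.1/1.67 = 1.26, or 2.05/1.67 = 1.23 to 2.15/1.67 = 1.29 if 2.1 is a rounded value. At 1.28 the cumulative cut is 1 − 1.28/3.1 = 58.7%, against 1 − 1.7/3.1 = 45.2%.
2. *First reduction from 4.4 mg/kg.* The 25% rule gives 4.4 × 0.75 = 3.3. The preceding level is 3.1 (3.1/4.4 − 1 = −29.5%) if DL-6A is taken as the level before 7A-2.
3. *Combination started at the lowered run-in dose, 3.1 × 0.75 = 2.325 mg/kg.* The 25% rule gives 2.325 × 0.75 = 1.744. If 2.3 is not a Figure 9 level and DL-5A is read as the preceding one, Section 5.8.1 gives 2.1, a cut of 1 − 2.1/2.325 = 9.7% (8.7% from the rounded 2.3). The synopsis rule is then the larger cut, the reverse of the first-reduction result.

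**The case against.** The fair case against accepts the mismatch and disputes its weight.

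- *The demonstrated gap is small.* It is 0.2 mg/kg at the first step, the analyses are descriptive, and Section 5.8.1 requires Medical Monitor agreement on how a patient continues after a DLT. This stands as a limit on size. It does not settle the rule, because the Medical Monitor works from the same two texts.
- *PTCL and combination patients may have different rules by design.* PTCL has its own section with its own hematologic thresholds. That is right. The contrast at 3.1 mg/kg is context, and the contradiction is only between synopsis and body. How often each rule appears is no evidence about which is correct.
- *The conditional figures are uncertain.* This also stands. The ladder is approximate, the Safety Review Committee may adjust steps, and DR-A-2 begins at level 7, so using DL-6A as its predecessor is a choice. The reversal needs an ALRN-6924 cut in the run-in and two assumptions about Figure 9. None of these figures is needed for the conclusion.
- *The combination cohort is not the only group affected.* Section 5.7.1 ends escalation in DR-A and DR-A-2 but not treatment there, and does not say that DR-B escalation is over. Those patients remain under the conflicting Phase 1 rules, and no figure shows how many in any group would be re-treated.

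The run-in's 25% steps might seem to resolve the matter, but they set a cohort's starting dose, not an individual's dose after toxicity.

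**Conclusion.** The concern holds. The synopsis and Section 5.8.1 give different re-treatment doses for the same event, and the combination cohort is directed to both. The firm size is 2.3 against 2.1 mg/kg at the first reduction from 3.1 mg/kg, resting only on printed doses and on reading DL-5A as the level preceding DL-6A. The wider gap at the second reduction, the 4.4 mg/kg comparison and the reversal after a lowered run-in dose are conditional on Figure 9. If the reversal is real, neither text is always the more cautious, so a site could not resolve the conflict simply by following the more conservative text.

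The effect is confined to re-treated patients and their later tolerability data. This should be corrected, but it does not undermine the trial's DLT decisions. Nothing here indicates which rule or dose is right.

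**What to change.** Reconcile four places: the synopsis Phase 1 dose-modification text, the synopsis combination text, Section 5.8.1 and Section 5.8.3. The sponsor's clinical team should choose one re-treatment rule and state it in the same words in the synopsis and the body. The amended text should also say how the rule applies to combination patients whose starting dose was lowered in the run-in, since a preceding level may not be defined for them.

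The same amendment could tidy one editorial point: the dose-modification sections sometimes discontinue the patient from the study and sometimes only from study treatment. Section 6.13 already keeps Phase 2 patients on study for survival follow-up, so no loss of survival data is shown.

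The cost is amendment wording and a letter to sites, with no new procedures.

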5.4.1.1 Management of Infusion-Related Reactions

For the management of Grade 1-2 infusion-related reactions:

- Stop the infusion for 15–30 minutes.
- Measure vital signs at least once every 5 minutes until symptoms abate.
- Consider administering diphenhydramine 25–50 mg IV or equivalent.
- If symptoms abate, re-start the infusion at one-half the previous rate.
- Additional medical measures, such as the administration of selective anti-histamines (e.g., cimetidine 300 mg or ranitidine 50 mg IV) or corticosteroids (e.g., dexamethasone 20 mg IV) may be considered for reactions that do not abate after 15 minutes.
- If symptoms do not abate 30 minutes after the administration of medical measures, discontinue the day's ALRN-6924 treatment.

In the case of a prior infusion-related reaction controlled by above medical management, subsequent ALRN-6924 infusions should include premedication at least 30 minutes before the start of ALRN-6924 infusion.

For the management of Grade 3+ infusion-related reactions:

- Stop the infusion.
- Measure vital signs at least once every 5 minutes until symptoms abate.
- Consider administering the following:
 - Diphenhydramine 50 mg IV
 - Cimetidine 300 mg or ranitidine 50 mg IV
 - Dexamethasone 20 mg IV
 - Epinephrine 0.5 mg SC
 - Albuterol inhaler as needed for bronchospasm
- Additional agents may be administered per institutional guidelines for the treatment of infusion-related reactions.

Patients experiencing Grade 3 hypersensitivity reactions that require hospitalization or any Grade 4 hypersensitivity reactions that are related to ALRN-6924 infusion should be discontinued from study treatment and not rechallenged.

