Adverse events considered for dose reduction should not include the events assessed by the Investigator as exclusively related to underlying disease or other medical condition or concomitant treatment. A patient who experiences an AE considered related to ALRN-6924 that does not meet the requirement for discontinuation may continue on study if the patient is receiving clinical benefit and/or the Investigator feels continued participation is in the best interest of the patient. In such cases, at the Investigator's discretion and in agreement with Sponsor's Medical Monitor, the dose for a patient may be reduced as described above.

A patient who experiences a DLT must continue treatment at a reduced dose level, or discontinue ALRN-6924 treatment (if Grade 4 related AE), as described above at the discretion of the Investigator and in agreement with Sponsor's Medical Monitor until disease progression or unacceptable toxicity. Once the dose has been reduced for a patient, it may not be re-escalated.

5.8.2 Dose Modifications – Phase 2a dose expansions in PTCL (ALRN-6924 administered as single agent therapy)

In the event a non-hematologic Grade 4 AE considered related to ALRN-6924 is observed, the patient must be discontinued from the study. Exceptions include emesis, diarrhea or electrolyte abnormalities that resolve within 2 days on optimum treatment. For these exceptions, treatment may be delayed for up to 2 weeks to allow resolution of the toxicity (i.e., return to Grade ≤ 1 or baseline), followed by re-treatment at a reduced dose. Relevant labs should be repeated as medically indicated.

In the event a non-hematologic Grade 3 AE considered related to ALRN-6924 is observed (exceptions are Grade 3 fatigue, nausea, emesis, diarrhea or clinically insignificant electrolyte abnormalities that resolve within 2 days on optimum treatment), treatment may be delayed for up to 2 weeks to allow resolution of the toxicity, followed by re-treatment at a reduced dose. Relevant labs should be repeated as medically indicated.

For hematologic toxicities, patients must discontinue treatment with ALRN-6924 if

- Neutrophil counts $< 0.5 \times 10^9/L$ for > 5 days, or
- Platelet counts $< 10 \times 10^9/L$, or
- Hemoglobin $< 6\text{g/dL}$ (despite RBC transfusion or Erythropoiesis-Stimulating Agent (ESA) administration)

Patients must interrupt treatment if

- Neutrophil counts $< 0.5 \times 10^9/L$ for ≤ 5 days, or

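### The DLT sentence in Protocol 5.8.1 says to continue at a reduced dose after a Grade 3 infusion hypersensitivity reaction requiring hospitalization, which 5.4.1.1 says must not be rechallenged

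*Protocol*

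**What the plan says.** Section 5.4.1.1, on infusion-related reactions, is not limited to any cohort. It says that "Patients experiencing Grade 3 hypersensitivity reactions that require hospitalization or any Grade 4 hypersensitivity reactions" related to the ALRN-6924 infusion "should be discontinued from study treatment and not rechallenged".

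Section 5.9.2 counts an infusion reaction as a DLT if it is Grade 3 and caused hospitalization, or if it is Grade 4. It adds that the DLT criteria guide reduction, interruption or discontinuation for individual patients throughout the trial. Only Cycle 1 DLTs inform escalation.

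Section 5.8.1 has three relevant rules:

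- **Related Grade 4 AE:** "In the event a Grade 4 AE considered related to ALRN-6924 is observed, the patient must be discontinued from study treatment". Its exceptions do not include hypersensitivity.
- **Related Grade 3 AE:** treatment may be delayed by up to 2 weeks and then resumed at a reduced dose. The "exceptions are Grade 3 fatigue, nausea, emesis, diarrhea or clinically insignificant electrolyte abnormalities that resolve within 2 days on optimum treatment". A later line on the re-treatment dose is qualified by the words *as permitted*.
- **DLT:** "A patient who experiences a DLT must continue treatment at a reduced dose level, or discontinue ALRN-6924 treatment (if Grade 4 related AE"). The sentence goes on "as described above at the discretion of the Investigator and in agreement with" the Sponsor's Medical Monitor, "until disease progression or unacceptable toxicity".

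The sentence before the DLT rule says that a patient with a related AE "that does not meet the requirement for discontinuation may continue on study" if there is clinical benefit or the investigator judges it best for the patient.

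The synopsis repeats the Grade 3 and DLT rules but not the stop in 5.4.1.1. Section 5.8.3 applies 5.8.1 to the palbociclib combination cohort. Section 5.8.2 (PTCL) has a similar non-hematologic Grade 3 paragraph but no DLT sentence.

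**The concern.** One event is covered by two instructions that do not match. The section written for the reaction says stop and do not give the drug again. The dose-adjustment section says that a patient with a DLT must carry on at a lower dose, and it names stopping only for Grade 4. It neither cites 5.4.1.1 nor says which section prevails.

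What is at stake is a decision for a single patient: no further ALRN-6924, or re-exposure at a reduced dose after a reaction serious enough for hospital. Infusion reactions were already a recognized issue in this trial. The synopsis says that DR-A-2 was explored to mitigate them.

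**Working it through.** No arithmetic applies. The check follows one event through the protocol: an ALRN-6924-related Grade 3 infusion hypersensitivity reaction requiring hospitalization.

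| Place | What it does with this event | Force |
|---|---|---|
| 5.4.1.1 | Discontinue, no rechallenge | *should* |
| 5.9.2 | Classifies it as a DLT | definition |
| 5.8.1, DLT sentence, and synopsis copy | Continue at a reduced dose; discontinuation named only for Grade 4 | *must*, with qualifiers |
| 5.8.1, Grade 3 paragraph, and synopsis copy | Delay up to 2 weeks, then a reduced dose; hypersensitivity not among the exceptions | *may* |
| 5.8.2, Grade 3 paragraph (PTCL), and synopsis copy | Same pattern | *may* |

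**Step 1: is the event a DLT?** Yes, by either route. It meets the infusion-reaction criterion in 5.9.2. If a site did not call it an infusion reaction, it would still be a related Grade 3 AE under the general definition.

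**Step 2: which branch of the DLT sentence applies?** The event is Grade 3, so it is outside the only discontinuation branch named. Literally, the reduced-dose branch remains, and that differs from 5.4.1.1.

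**Step 3: do the Grade 3 paragraphs also differ from 5.4.1.1?** No. They allow delay and re-treatment but do not require it, and the re-treatment dose lines in both sections carry *as permitted*. A site that follows 5.4.1.1 breaches nothing in them. They only omit the exception.

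**Step 4: does other text in 5.8.1 restore the stop?** Only in part. The requirement for discontinuation in the preceding sentence could mean 5.4.1.1. It could also mean 5.8.1's own triggers: a related Grade 4 AE, or AEs that persist after a 2-week delay or after the maximum number of reductions. A first Grade 3 reaction meets neither trigger.

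**Step 5: Grade 4 reactions.** Sections 5.4.1.1 and 5.8.1 both stop treatment, so they agree.

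**Step 6: who is under the rule?** The DLT sentence clearly covers dose escalation (about 75 planned). Escalation has ended in DR-A and DR-A-2, and the documents do not say how many of these patients remain on treatment. In the combination cohort (about 15-25 planned, from age 12), 5.8.3 brings in 5.8.1, so the Grade 3 paragraph applies. The reach of the DLT sentence there is uncertain: the synopsis heads the DLT definition as belonging to Phase 1 dose escalation, and 5.7.2 uses the Phase 1 DLTs only as a guide. These are planned enrolments, not patients affected.

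**The case against.** The strongest reply is that a sensible reader would never rechallenge:

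- Section 5.4.1.1 is the specific rule and names this exact event, so it should prevail over a general dose rule.
- The DLT sentence is subject to investigator discretion, Medical Monitor agreement and unacceptable toxicity, and 4.7 allows removal for unacceptable adverse events.
- Hospitalization makes the event a serious adverse event (8.1.2), reportable to the sponsor within 24 hours (8.4) and reviewed by the Medical Monitor (8.10.2). The sponsor would know well before a 2-week delay ran out.
- The contrast between *should* and *must* is weak evidence, because the protocol uses these verbs loosely. The palbociclib dose-modification rule is a plain directive in the synopsis and a *should* in 5.8.3.

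Most of this stands. It makes rechallenge unlikely, and it defeats the inference, which a reader might draw, that the protocol compels rechallenge or that a site cannot satisfy both sections. The qualifiers leave room to stop. A reader might also infer that the Grade 3 paragraphs contradict 5.4.1.1; their permissive wording and the *as permitted* qualifier do not support that.

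What remains is that every one of these routes permits stopping and none prohibits giving the drug again. The DLT sentence still reads the wrong way for this event, and its synopsis copy stands without the stop rule.

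**Conclusion.** The point holds as an inconsistency of wording, confined to one sentence (and its synopsis copy) and one event. The DLT sentence of 5.8.1 does not match the stop in 5.4.1.1. The Grade 3 paragraphs of 5.8.1 and 5.8.2 have only an omission.

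The size cannot be put in numbers. The documents give no rate for this reaction, so no count of affected patients is claimed. A reader might infer harm to the combination cohort, including its adolescents, but neither an event rate nor a certain reach of the DLT sentence supports that. A reader might also infer a distorted MTD or ORR. The event counts as a DLT under either instruction, so the MTD does not turn on it, and nothing in the documents shows an effect on ORR.

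The conclusion assumes that the DLT sentence is read as written and that a safety stop should not depend on readers working out which section prevails. Priority: minor safety-wording correction.

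**What to change.** Add to the DLT sentence of 5.8.1 and its synopsis copy: *except Grade 3 infusion-related hypersensitivity reactions requiring hospitalization, for which ALRN-6924 is permanently discontinued without rechallenge per Section 5.4.1.1*.

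Put the same cross-reference in the Grade 3 paragraphs of 5.8.1 and 5.8.2 and their synopsis copies. Section 5.8.3 then inherits it from 5.8.1. In 5.4.1.1, change *should* to *must*.

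That is 2 + 4 + 1 = 7 short edits at the next amendment, with no extra data, visits or patients. The downside is that a rare patient who might have tolerated a reduced dose is not re-treated, which 5.4.1.1 already intends.
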